- VAS (Incision Healing Assessment Form) 0-10 continuous, based on standardized digital image (1 week) and exam (2 and 5 weeks). The VAS can be completed by the PI, any of the sub-investigators, or any properly trained physicians or RN associated with the project. If the VAS is completed based on an incisional photo, study staff will collect the exact date the photo was taken.
- If the subject will not be returning 2 weeks postoperatively as standard of care, they will be asked to take another standardized digital image at 2 weeks, and the 2 week follow-up will be done over the phone.

SECONDARY OBJECTIVES

To assess complications between patients treated with either PICO or standard care dressings. **Outcome Measures:**

- Secondary: Daily phone calls for first week; follow-up appointments
 - Drainage amount
 - User-friendliness for patient
 - Complications
 - Return to OR
 - Need for antibiotics

Data Analysis:

- Compare TOTAL PICO vs. SOC incision appearance VAS and drainage amount using t-Test
- Compare Primary JA (joint arthroplasty) PICO vs. SOC incision appearance VAS and drainage amount using t-Test
- Compare Revision JA PICO vs. SOC incision appearance VAS and drainage amount using t-Test
- Compare TOTAL PICO vs. SOC for all other outcome measures using chi-square based on number in each category
- Compare Primary JA PICO vs. SOC for all other outcome measures using chi-square based on number in each category
- Compare Revision TJA PICO vs. SOC for all other outcome measures using chi-square based on number in each category
- Post-hoc assessment of risk factors – ASA level, surgeon, BMI

EVALUATION DESIGN

The study will comprise a prospective, open labeled, single-centre study to determine the efficacy of a Single-Use Negative Pressure Wound Therapy (NPWT) System (PICO) in the prevention of postsurgical incision healing complications in patients undergoing KA and THA. The study will be comparative and randomized according to a pre-determined randomization schedule. The study will be open-labeled due to the physical appearance of both the investigational product and standard dressings, which will be impossible to blind to both the investigator and/or patient. Patients will be stratified according to the type of surgical procedure (KA/THA) and primary or revision procedure. Patients will be followed up for a period of 5 weeks, to determine if there are any latent problems with infection or dehiscence.

PICO

IRB Project # 1208434

Version 8

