Days 1-7 (following surgery)	
Daily communication with the subject (in person or phone contact) to collect the following information:
 
○ Drainage amount○ User-friendliness for subject (including ease of use and subject's opinion of the noise associated with the PICO device.○ Assessment of Complications○ Assessment of return to OR○ Assessment of need for antibiotics

	
*On the days within this window that fall on a weekend or holiday, the subject will not be contacted, but rather asked for a summary of this information on the next business day. If the subject is unreachable despite the site's best effort for one or a number of the days in this window, the subject will be asked to give a summary of the "missed" days.

Day 7 (1 week postoperative, +/- 3 days)	
Incision appearance: Standard digital photo of the incision (taken by the subject, family member, friend, or caregiver). Subject will submit this photo to the site.
 
VAS (Incision Healing Assessment Form) will be completed based on photo of incision.

Day 14 (+/- 7 days)	
Incision appearance: Physician exam; VAS (Incision Healing Assessment Form); Drainage amount; Assessment of complications; Assessment of return to OR; Assessment of need for antibiotics.
 
(If the subject will not be returning 2 weeks postoperatively as standard of care, they will be asked to take another standardized digital image at 2 weeks, and the 2 week follow-up will be done over the phone.)

Day 35 (+/-14 days)	
Incision appearance: Physician exam; VAS (Incision Healing Assessment Form); Drainage amount; Assessment of complications; Assessment of return to OR; Assessment of need for antibiotics.
 
Functionality and Patient's QoL Assessment (SF12)

Study Completion	Reason for Study Completion

ADVERSE EVENTS

All adverse events reported spontaneously by the patient or in response to questioning or observation by the Investigator will be recorded.

ETHICS/IRB APPROVAL

Before the start of the trial the Investigator will submit the trial to the local independent Ethics Committee/Institutional Review Board (IRB) for review and approval.

PATIENT CONSENT

Before being recruited to the clinical trial, the patient must have given written informed consent to participate.

REFERENCES

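### User-friendliness, reported on days 1–7, goes to an unordered, unstratified chi-square on category counts, with no rule giving one value per patient

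*Combined protocol and SAP*

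**What the plan says.** Secondary Objectives lists user-friendliness among five secondary measures, under the line "Secondary: Daily phone calls for first week; follow-up appointments". The Days 1–7 row of the Treatment Regime schedule asks for "Daily communication with the subject (in person or phone contact) to collect the following information", and one of the listed items is "User-friendliness for subject (including ease of use and subject's opinion of the noise associated with the PICO device". The Day 14 and Day 35 rows do not repeat that item, so it belongs to the first week only.

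A footnote to the same row says "On the days within this window that fall on a weekend or holiday, the subject will not be contacted". A summary is taken on the next business day instead, and a patient who could not be reached later summarises the missed days.

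In Data Analysis, the t-test covers only incision VAS and drainage amount. Everything else follows three rules:

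- all patients: "Compare TOTAL PICO vs. SOC for all other outcome measures using chi-square based on number in each category"
- primary procedures: "Compare Primary JA PICO vs. SOC for all other outcome measures using chi-square based on number in each category"
- revisions: "Compare Revision TJA PICO vs. SOC for all other outcome measures using chi-square based on number in each category"

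User-friendliness therefore falls under all three. The documents give no response scale for it, no index day, no per-patient summary, and no ordinal or repeated-measures method. Evaluation Design says patients are stratified by KA/THA and by primary or revision procedure, but the overall chi-square does not use these strata.

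**The concern.** Two questions are left to whoever runs the analysis, in an open-label trial where the answers could be chosen after the data are seen.

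1. **What is counted.** A chi-square needs independent entries. The plan counts the number in each category without saying whether the unit is a patient or a report. If reports are the unit, one patient contributes several correlated entries and the test rejects too often.
2. **Whether order is used.** Answers about ease of use may well be graded. A Pearson chi-square on K categories spreads its power over K − 1 degrees of freedom, whereas a rank or proportional-odds test puts it on the one direction of interest, a shift towards easier or harder use.

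At stake is the patient-experience comparison. It could report a difference that is an artefact of repeated entries, or miss one that the same data could show. The item on device noise raises a further problem: it concerns PICO only, so standard care has nothing to set against it.

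**Working it through.** **Inputs from the documents.** 1,000 patients randomised 1:1, so about 500 per arm; user-friendliness collected on days 1–7; no contact on weekends or holidays. The plan gives no alpha, power or effect size, so it has no figure of its own to reproduce for this outcome.

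**Assumptions.** Two-sided 5%; 2 to 5 response categories; within-patient correlation 0.3–0.7 on an underlying normal scale; a proportional-odds shift between arms.

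**Step 1: number of reports per patient.** Any seven consecutive days contain one Saturday and one Sunday, so there are at most 7 − 2 = 5 contact days. Seven entries arise only if a summary is recorded separately for each day it covers, which the plan does not say. Both cases are shown in step 3.

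**Step 2: cost of ignoring order, one value per patient.** An ordered 1-df test has 80% power at noncentrality λ = (1.960 + 0.842)² = 7.85. If the difference is a pure shift, the chi-square has about the same λ but K − 1 degrees of freedom. Its power is P(χ²(K − 1, λ = 7.85) > 5% critical value). The sample-size cost is the λ needed for 80% power on K − 1 df, divided by 7.85.

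| Categories | df | Critical value | Power at λ = 7.85 | λ for 80% | Ratio |
|---|---|---|---|---|---|
| 2 | 1 | 3.84 | 80% | 7.85 | 1.00 |
| 3 | 2 | 5.99 | 71% | 9.63 | 1.23 |
| 4 | 3 | 7.81 | 64% | 10.90 | 1.39 |
| 5 | 4 | 9.49 | 60% | 11.94 | 1.52 |

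A second route uses 500 per arm, equal control categories and an assumed odds ratio of 1.37. Here λ = 500 × Σ(p − p̄)²/p̄ over both arms and all categories, compared with a midrank score test:

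| Categories | Chi-square | Ordinal test |
|---|---|---|
| 2 | 0.70 | 0.70 |
| 3 | 0.67 | 0.77 |
| 4 | 0.64 | 0.79 |
| 5 | 0.60 | 0.80 |

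With five categories the pair is 0.32 and 0.51 at an odds ratio of 1.25, and 0.84 and 0.95 at 1.5. The two routes agree: there is no loss with two categories, and about 10 to 20 power points are lost with three to five categories near 80% power.

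**Step 3: size if every report were counted.** Simulation with no treatment effect and 500 per arm. Each report is √ρ × (patient term) + √(1 − ρ) × (report term), both standard normal, cut into equal categories. A Pearson chi-square is then run on the pooled counts at nominal 5% (3,000 runs per cell).

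| Categories | Reports | ρ = 0.3 | ρ = 0.5 | ρ = 0.7 |
|---|---|---|---|---|
| 2 | 5 | 13.4% | 19.9% | 26.2% |
| 3 | 5 | 14.9% | 21.2% | 28.9% |
| 5 | 5 | 12.3% | 20.0% | 31.5% |
| 2 | 7 | 19.5% | 25.8% | 33.0% |
| 3 | 7 | 19.1% | 28.5% | 38.7% |
| 5 | 7 | 17.7% | 29.3% | 41.4% |

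The simulation error of a cell near 30% is √(0.3 × 0.7/3,000) ≈ 0.8 points, and repeat runs move cells by a point or so. I quote the ranges as about 12–30% for five reports and 16–42% for seven. At ρ = 0, or with one value per patient, the size is about 5%.

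**The case against.** The strongest reply is that a chi-square on one entry per patient is valid and holds its level, and that the plan can be read that way. The other outcomes under the same rule (complications, return to OR, antibiotics) read naturally as one entry per patient. Preferring an ordinal test is then a question of efficiency, on one of five secondary measures. All of this stands, and it limits the point. It does not close it, because those outcomes become ever/never without further rules, whereas several daily opinions do not become one value without a stated rule.

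Four stronger readings are tempting and are not supported:

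- **That the ratings are ordered.** No scale, number of categories or response format is given. Graded answers are plausible, but a yes/no item has no order to lose.
- **That the plan pools the daily reports.** It neither says so nor rules it out.
- **That the comparison is worse than it need be either way.** A yes/no item counted once per patient loses nothing from the unordered test.
- **That pooling would push the size to 50–77%.** This comes from dividing the 4-df statistic by 1 + (7 − 1) × ICC, which is 2.8 at 0.3 and 5.2 at 0.7, as if all four components were inflated equally. When one patient tendency drives graded answers, the components other than the overall shift are less correlated within patient, and the simulated five-category size with seven reports is about 16–42%. It also presumes seven entries per patient, whereas the footnote allows at most five contact days.

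**Conclusion.** The point holds in a conditional form. What the documents establish is that user-friendliness is collected repeatedly over days 1–7, is assigned to an unordered, unstratified chi-square on counts, and has neither a defined scale nor a rule for one value per patient.

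The consequence depends on two things the plan leaves open:

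- If the scale is graded with 3–5 categories and each patient counts once, the test keeps its level but gives up power equivalent to about 23–52% more patients. If the item is yes/no, it gives up nothing.
- If every report is counted, the 5% test has a true size of about 12–30% (five reports) or 16–42% (seven), on the assumed correlation of 0.3–0.7. This applies to a yes/no item as well.

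This is more than missing detail, because a better method is available from the same data and loses nothing if the item proves to be yes/no. It concerns a secondary outcome only. The primary VAS comparison is unaffected.

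**What to change.** In Data Analysis, take user-friendliness out of the three chi-square bullets and state instead:

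1. The response scale for ease of use.
2. One ease-of-use value per patient, for example the median of the available day 1–7 reports. A next-business-day or missed-day summary counts as one report. Add a rule for a median that falls between two categories.
3. A comparison of arms by a van Elteren test or a proportional-odds model, stratified by KA/THA and primary/revision. With a yes/no item this becomes a Cochran-Mantel-Haenszel test.
4. The device-noise item summarised descriptively in the PICO arm only.

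The cost is analysis-plan wording; no patients, visits or data are added. The downside is that day-to-day detail moves to a descriptive table.

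### At least 15 unranked secondary tests, nine of which could each be cited for the complication-prevention aim: about a 26% chance of a false positive among those nine, about 14% in PICO's favour

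*Combined protocol and SAP*

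**What the plan says.** All of this is in the combined protocol and SAP.

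- **Secondary Objectives** lists five outcomes: drainage amount, user-friendliness, complications, return to OR and need for antibiotics. Their timing is given only as "Secondary: Daily phone calls for first week; follow-up appointments".
- **Data Analysis**, total population: drainage shares a line with the primary outcome, "Compare TOTAL PICO vs. SOC incision appearance VAS and drainage amount using t-Test". The other four secondaries fall under "Compare TOTAL PICO vs. SOC for all other outcome measures using chi-square based on number in each category".
- **Data Analysis**, subgroups: the same tests are repeated for primary and for revision procedures, the latter as "Compare Revision TJA PICO vs. SOC for all other outcome measures using chi-square based on number in each category" and, for drainage, "Compare Revision JA PICO vs. SOC incision appearance VAS and drainage amount using t-Test".
- **Data Analysis**, last line: "Post-hoc assessment of risk factors – ASA level, surgeon, BMI". This is the only analysis given a label that lowers its standing.
- **Evaluation Design** states the purpose as "to determine the efficacy of a Single-Use Negative Pressure Wound Therapy (NPWT) System (PICO) in the prevention of postsurgical incision healing complications". It also makes primary versus revision a stratification factor and describes the trial as open-label.

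The primary outcome is an incision-appearance VAS, not complications. Nowhere does the document give a significance level, sidedness, testing order, alpha allocation or multiplicity adjustment.

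**The concern.** Unadjusted secondary tests are common and often harmless, because the primary outcome carries the main conclusion. Here the primary outcome is an appearance score, while the stated purpose is to show that the device prevents complications. The evidence for that purpose can come only from the secondary outcomes.

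Three of the five bear on it directly: complications, return to OR and need for antibiotics. Each is tested in the total population, in primary procedures and in revisions. The nine results may disagree, and the plan does not say which one governs. A report could therefore lead with whichever favourable p-value appeared, for instance fewer antibiotic courses in revisions alone, and nothing in the plan would mark that as a weaker finding than complications overall. The error rate of a prevention conclusion reached in this way is not 5%.

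**Working it through.** The plan states no family-wise error rate, so there is no figure to reproduce.

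**Count of tests (from Data Analysis).** Drainage by t-test is 1 outcome × 3 populations = 3. User-friendliness, complications, return to OR and antibiotics by chi-square are 4 × 3 = 12. Together 3 + 12 = 15. The subset bearing on complication prevention is 3 × 3 = 9. Both are minimum counts: information is collected daily in week 1 and, except for user-friendliness, again at Days 14 and 35 (Treatment Regime table), and no analysis time point is fixed.

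**Assumptions (not in the documents).**
- Two-sided 0.05 per test, hence 0.025 in PICO's favour.
- Correlation between outcomes of 0.5, varied over 0 to 0.8.
- Share of primary procedures of 80%, varied over 50% to 90%.
- No true effect on any outcome.

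**Reference points that need no correlation.**
- Expected number of false positives: 15 × 0.05 = 0.75 and 9 × 0.05 = 0.45; in PICO's favour 15 × 0.025 = 0.375 and 9 × 0.025 = 0.225.
- If all tests were independent, the chance of at least one would be 1 − 0.95^15 = 53.7% and 1 − 0.95^9 = 37.0%; in PICO's favour 1 − 0.975^15 = 31.6% and 1 − 0.975^9 = 20.4%.

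Independence cannot hold, because the total population is made up of the two subgroups. The independent-test figures are therefore too high.

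**Allowing for the overlap.** For each outcome, draw null statistics Z_P (primary) and Z_R (revision) independently of each other, correlated across outcomes. With f the share of primary procedures, set

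Z_T = √f · Z_P + √(1 − f) · Z_R.

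Count a false positive in either direction if any |Z| > 1.96, and one in PICO's favour if any Z > 1.96. With 400,000 replicates per setting:

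| Tests | Either direction, central case | Range | PICO's favour, central case | Range |
|---|---|---|---|---|
| 15 (five outcomes, three populations) | 37% | 26–46% | 19% | 13–26% |
| 9 (three outcomes, three populations) | 26% | 20–31% | 14% | 10–16% |
| 5 (five outcomes, total only) | 18% | 13–23% | 9% | 6–12% |
| 3 (three outcomes, total only) | 13% | 10–14% | 6% | 5–7% |
| 1 (one outcome, total only) | 5% | – | 2.5% | – |

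The central case is correlation 0.5 and 80% primary procedures.

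**Check with binary data.** Pearson chi-square tests on simulated binary outcomes (500 per arm, 80% primary, latent correlation 0.5 or 0.8, assumed event rates of 10%, 3% and 10%, or 19%, 5% and 15%) gave 26–30% in either direction for the nine tests and 13–14% for the three in the total population. The normal approximation is adequate for this purpose.

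**The case against.** The strongest reply has three parts.

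*The list is not entirely flat.* The plan separates primary from secondary, words the secondary objective in terms of complications, lists the total population first, and uses primary versus revision as a prespecified stratum rather than a subgroup found in the data. All of this is true and counts in the plan's favour. It is still not a rule on which result governs, and prespecifying a subgroup does not control the error rate across subgroups.

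*The plan has no success rule.* Nowhere does it say that one significant secondary or subgroup result demonstrates efficacy, and the secondary objective only sets out to assess complications. This also stands. The concern is that the plan leaves such a claim open, not that it makes one. The efficacy wording in Evaluation Design is why the opening matters.

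*The size is easily overstated.* A reader might infer from the 37% that a chance finding in favour of PICO is likely. The documents do not support that. The 37% counts errors in both directions over all 15 tests, including drainage and user-friendliness, which do not bear directly on complication prevention. In PICO's favour the figure is about 19%, and for the nine relevant tests about 14%. A reader might likewise take the independent-test figure of 54%, but the total population contains both subgroups, so the tests are not independent.

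**Conclusion.** The concern holds as a gap in the plan: at least 15 secondary tests without rank or label, nine of which could each be cited for the trial's stated aim. For those nine, the chance of at least one false result in PICO's favour is about 14%, between five and six times the 2.5% of a single test (0.136 / 0.025 = 5.4). In either direction it is about 26% against 5%. A false favourable result is therefore materially more probable than the nominal level suggests, but in none of the settings examined is it more likely than not.

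The count comes straight from the document. The percentages rest on an assumed alpha, outcome correlation and primary-procedure share, and the ranges show how far they move. Analysing several time points would raise them further. The gap remains whichever visit is chosen for the primary VAS.

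**What to change.** Add to Data Analysis, in substance:

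- Complications in the total population, counted once per patient over the 5-week follow-up, is the only secondary comparison that can support a claim about preventing complications. It is tested at two-sided 0.05.
- All other secondary comparisons, and all Primary JA and Revision JA comparisons, are exploratory. They are reported as estimates with 95% confidence intervals and support no efficacy claim.

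Counting each patient once removes the choice among daily, Day 14 and Day 35 data. With one governing test, the error rate of the prevention claim returns to 5% (2.5% in PICO's favour).

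Do not make this test conditional on the primary VAS. The VAS is assessed at 1, 2 and 5 weeks and compared in three populations, with no single primary comparison named, so there is nothing defined to open such a gate. Gating would also put the trial's stated aim behind an appearance score in an open-label study.

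The cost is a few sentences, with no new data, patients or staff. The small downside is that an isolated significant result on another secondary outcome or in a subgroup can no longer be claimed as evidence of efficacy.

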that incisions are covered with a postsurgical cover dressing, for up to a period of 48 hours, to help control postoperative bleeding, absorb exudate, provide mechanical protection, help to reduce edema and provide protection from exogenous sources (Mangram *et al* 1999). Multiple patient comorbidities, environmental factors and the type and length of surgery may elevate certain groups of patients into a higher level of risk of developing a post-surgical complication: calling for a higher degree of vigilance and postsurgical intervention. Surgical complications include; wound dehiscence, infection (deep or superficial), hematomas, seromas, tissue necrosis and delayed incision healing. Complication rates can range from 19% in patients requiring open reduction and internal fixation (ORIF) of tibial plateau, pilon and calcaneus fractures (Stannard *et al* 2011) up to 50% in high energy trauma wounds (Stannard *et al* 2006). These complications can have a high degree of morbidity for the patient and further sequelae may result in additional surgical procedures or revisions, a lower functional status for the patient, an increased in length of hospital stay (LOS) and a higher cost for the healthcare provider.

Traditional NPWT has been shown to be an effective adjunct therapy in the treatment of acute and chronic wounds, but the emergence of incisional NPWT (iNPWT) and supporting evidence is growing momentum. *In vitro* studies have shown that iNPWT may help to improve the stimulation of blood flow, help manage exudate, help to reduce edema, provide a mechanical and “splinting” effect on the incision and provide mechanical protection from the environment. Its impact on the prevention or reduction of post-surgical incision complications is still in its infancy, but recent studies pioneered by Stannard *et al* (Stannard 2011) have been encouraging and have demonstrated a statistically significant reduction in infection and dehiscence in patients considered as high-risk following severe skeletal trauma.

The aim of this study is to assess the prevention of incision healing complications in patients undergoing KA and THA treated with either Single-Use Incisional NPWT compared to standard of care dressings.

PRIMARY OBJECTIVE

Compare PICO wound dressing to current MOI standard of care for postoperative incision management in Knee Arthroplasty (KA) or Total Hip Arthroplasty (THA) patients.

Outcome Measures:

- Primary: Incision appearance at 1, 2 and 5 weeks postop

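### The stated aim is prevention of incision complications, but the only primary outcome is incision appearance, and the secondary complication comparison is loosely defined and unstratified

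*Combined protocol and SAP*

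**What the plan says.** The background section closes with "The aim of this study is to assess the prevention of incision healing complications in patients undergoing KA and THA", and EVALUATION DESIGN repeats that the study is "to determine the efficacy of a Single-Use Negative Pressure Wound Therapy (NPWT) System (PICO) in the prevention of postsurgical incision healing complications".

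The outcomes are set differently. Under PRIMARY OBJECTIVE the outcome is "Primary: Incision appearance at 1, 2 and 5 weeks postop", scored as "VAS (Incision Healing Assessment Form) 0-10 continuous, based on standardized digital image (1 week) and exam (2 and 5 weeks"). The test is "Compare TOTAL PICO vs. SOC incision appearance VAS and drainage amount using t-Test".

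Complications come under SECONDARY OBJECTIVES: "To assess complications between patients treated with either PICO or standard care dressings". They are listed as one item, next to return to OR and need for antibiotics. The only analysis line that reaches them is "Compare TOTAL PICO vs. SOC for all other outcome measures using chi-square based on number in each category", repeated for primary and for revision arthroplasty. Complication types are named only in the background: "Surgical complications include; wound dehiscence, infection (deep or superficial), hematomas, seromas, tissue necrosis and delayed incision healing".

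EVALUATION DESIGN stratifies patients by KA/THA and by primary or revision procedure. ASSIGNING PATIENTS TO TREATMENT gives bilateral patients the same dressing on both sides, without saying whether they count once or twice.

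**The concern.** The question that the trial says it answers and the outcome that it makes primary are different. A VAS of how the incision looks may move without any change in the number of patients who have an infection, dehiscence or hematoma. The comparison that does bear on prevention has no defined variable, no counting rule and no stated priority.

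Two things are at stake. A favourable appearance result could be read against an aim worded as prevention. A real difference in complication rate could be diluted, or the definition settled only after the data are seen, because several constructions fit the present wording: any type, each type, or one table of types.

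**Working it through.** **What needs no arithmetic.** Aim and design statement: prevention of complications. Primary outcome: appearance, compared by t-test. Complications: secondary, chi-square by category. Strata: KA/THA and primary/revision. The chi-square in all patients uses none of these strata. The separate primary and revision comparisons split on one factor, but they do not give one stratified estimate, and KA/THA enters nowhere.

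**Inputs for an illustration.** From the documents: 1000 patients and 1:1 allocation, so n = 500 per arm. Assumed because not given: two-sided 0.05, no dropout, the complication rate and the size of effect. The only rates in the documents, 19% to 50%, are for fracture and trauma wounds. The 1000 comes with no inputs and cannot be reproduced.

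**1. Sensitivity of the VAS.** Difference detectable with 80% power, in SD units: (1.960 + 0.842) × √(2/500) = 0.18. With an assumed SD of 2 points this is 0.35 points. A small difference in appearance can reach significance, and this says nothing about complications.

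**2. Types in one table versus one yes/no outcome.** Let pc and pt be the total complication rates, m their mean, and let complications split equally over six mutually exclusive types with the same relative reduction. The noncentrality is then the same for both tests: λ = n(pc − pt)² / [2m(1 − m)]. The yes/no test spends it on 1 degree of freedom (critical value 3.84), the seven-category table (none plus six types) on 6 (critical value 12.59). With a halving:

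| Control rate | λ | Power, yes/no | Power, seven categories | Expected count per type per arm |
|---|---|---|---|---|
| 5% | 500 × 0.025² / (2 × 0.0375 × 0.9625) = 4.33 | 54.8% | 29.1% | 3.1 |
| 10% | 500 × 0.05² / (2 × 0.075 × 0.925) = 9.01 | 85.1% | 59.0% | 6.3 |
| 19% | 500 × 0.095² / (2 × 0.1425 × 0.8575) = 18.46 | 99.0% | 91.9% | 11.9 |

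At 5% the small expected counts also make the chi-square approximation doubtful. A patient with two types would enter such a table twice, so the counts would not be independent. If each of six types were tested separately at 0.05, the chance of at least one false positive would be 1 − 0.95⁶ = 26.5% for independent tests.

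**3. When the composite does worse.** Suppose six independent types, each with control rate p, and PICO halves only two. The any-complication rates are 1 − (1 − p)⁶ and 1 − (1 − p)⁴(1 − p/2)². Power is from the pooled two-proportion formula:

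| p per type | Any complication, control vs PICO | Power, any complication | Power, one affected type |
|---|---|---|---|
| 1% | 5.9% vs 4.9% | 9.8% | 14.8% |
| 2% | 11.4% vs 9.6% | 15.3% | 25.5% |
| 3% | 16.7% vs 14.1% | 20.5% | 35.9% |

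The ranking reverses. The gain from one combined outcome depends on the effect being shared across types.

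**The case against.** The formal objectives are more modest than the aim. The primary objective only compares PICO with standard care for managing the incision after surgery, and complications have their own secondary objective and test. Appendix 2 says that the VAS form represents incision healing, and delayed healing is one of the listed complications, so the VAS is not unrelated to the aim. Complications sit beside two items that are naturally yes/no, and the secondary objective speaks of patients, so a per-patient yes/no reading is plausible. No text makes the background types into analysis categories.

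Much of this stands. A reader might infer that complications have no planned test; that is wrong, because the general chi-square line covers them in all patients. A reader might infer that the plan loses a known amount of power, or that 1000 patients are too few; the documents give no arthroplasty complication rate, and the loss in step 2 vanishes under the yes/no reading. A reader might also infer that the sponsor intends to report the VAS as prevention; nothing in the plan says so.

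The objection does not remove the mismatch. Two separate statements make prevention the question, overlap with one complication does not turn an appearance score into a complication rate, and under every reading the comparison in all patients leaves out the randomisation strata.

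**Conclusion.** The point holds in limited form. Without any assumption: the appearance VAS cannot by itself carry a conclusion about preventing complications, no defined comparison is designated to carry it, and the planned chi-square ignores the stratification. Conditionally: if category means complication type, the test is of pattern rather than rate, and patients with two types are counted twice.

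The power figures illustrate that second reading only. They rest on assumed rates, a two-sided 0.05 level, and an equal halving of six exclusive types. Under those assumptions the loss is about 26 percentage points at control rates of 5% and 10% and about 7 at 19%. The effect of ignoring the strata is not quantified, since no stratum rates are given. The randomised comparison itself is not in question. This should be changed, and the change is cheap.

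**What to change.** Keep the VAS as primary if wished. Then:

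- Define one yes/no outcome per patient: any incision complication through the final visit, with bilateral patients counted once.
- Compare it once in all patients, with a Mantel-Haenszel risk difference and 95% CI across the randomisation strata.
- Label it the key secondary comparison, and do not make it conditional on the VAS. The VAS has three time points and no single primary test, so a gate would be undefined, and a missed VAS would block the comparison that serves the aim.
- State that any conclusion about prevention rests on this comparison and not on the VAS.
- Report individual types descriptively.

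The cost is mainly wording, since TREATMENT REGIME already assesses complications daily in the first week, at Day 14 and at Day 35. It does not show that types are defined or recorded, so the list of qualifying complications must be written down and the form may need a field. There are three drawbacks. A composite weighs mild and severe types alike. It loses power if PICO affects only some types (step 3). And the final visit, Day 35 ± 14, falls anywhere from day 21 to day 49, so follow-up length varies between patients and should be reported by arm.
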